7.13 INJECTION SITE REACTION ASSESSMENT

At each treatment visit that occurs at the clinical site, an injection site reaction assessment will be made for the current and previous injection sites. Injection site reaction assessments are recorded

by the Investigator starting after the first injection is given. Refer to [sections 9.1.8](#) and [16.3](#) for more details.

7.14 COVID-19 GUIDANCE

The purpose of this guidance is to inform sites how to proceed in light of the challenges faced by patients and clinical trial sites as a result of COVID-19 shelter-in-place mandates from state governments. The content of this letter is based on FDA Guidance on Conduct of Clinical Trials of Medical Products during COVID-19 Pandemic (18 Mar 2020).

- The current schedule of assessments requires subjects to visit the clinic at least once every four weeks for lab assessments. Subjects may still continue to receive treatment with PRO 140 if they are unable to visit the clinic.
- Site staff may visit subjects' homes to conduct study assessments and/or deliver PRO 140.
- Sites may ship PRO 140 to subjects' homes if subjects are unable to visit the clinic.
- If subjects are unable to visit the clinic at least once every four weeks lab assessments will be missed. If this occurs site staff should contact subjects weekly by phone to assess:
 - Compliance to study treatment
 - Potential adverse events
 - Changes in concomitant medications
- Sites should document phone calls and include confirmation of compliance to study treatment, and report any adverse events and/or changes in medications.
- Subjects who report positive tests results for COVID-19 should have the diagnosis recorded as an adverse event.
- Sites should clearly document reasons for failing to obtain required assessments (e.g., limitation imposed by COVID-19 leading to the inability to perform the protocol-specified assessment).
- Any changes in the study visit schedule or missed visit should be entered as protocol deviation in the EDC and reason should be documented as missed study visit or visit performed out of window period due to COVID-19.
- If subject is early withdrawn from the study due to COVID-19, the reason should be clearly documented in the End of Study (EOS) section in EDC as "study discontinuation due to COVID-19".

- Monitoring activities will be performed remotely until Centers for Disease Control (CDC) recommendations allow travel to resume.

8 STATISTICAL CONSIDERATIONS

This section presents general information about statistical considerations and concepts such as statistical power, sample size, and a brief discussion on analysis methodology, as well as some data conventions. Detailed descriptions of the statistical analysis methods and data conventions that will be used in this study will be in a separate document; i.e., the Statistical Analysis Plan (SAP).

8.1 TREATMENT GROUPS

This is a single arm study. All eligible subjects will receive PRO 140 as a 700mg subcutaneous injection weekly until one of the following occurs:

- virologic failure
- consent withdrawn
- PRO 140 is approved
- CytoDyn decides to discontinue its development

Note: Subjects enrolled prior to Protocol v4.0 may still be receiving the original 350mg dose and have the option of increasing their dose to 700mg.

8.2 DESCRIPTION OF SAFETY MEASURES

The following safety measures will be assessed in this study.

1. Mean change in viral load (HIV-1 RNA levels) at the conclusion of the treatment period
2. Mean change in CD4 cell count at the conclusion of the treatment period
3. Emergence of Dual/Mixed (D/M)- and CXCR4-tropic virus in patients who had exclusive CCR5-tropic virus at study entry.
4. Tolerability of repeated subcutaneous administration of PRO 140 as assessed by investigator-evaluation of injection site reactions
5. Frequency of treatment-related adverse events resulting in study drug discontinuation
6. Frequency of Grade 3 or 4 adverse events as defined by the DAIDS Adverse Event scale
7. Frequency of treatment-emergent serious adverse events

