9.1.3 DAIDS AE Grade (Severity) Assessment

The investigator will carefully evaluate the comments of each subject and the response to treatment in order to judge the true nature and severity of the AE. The question of the relationship of AEs to study drug should be determined by the investigator after thorough consideration of all available facts. To assess severity, the investigator will use the DAIDS AE grading table (for adverse events as well as any injection site reactions refer to [Section 16.2](#) and [Section 16.3](#)).

The general guidelines for assessing the AE grade appear below. Full guidelines may be obtained at http://rsc.tech-res.com/Document/safetyandpharmacovigilance/DAIDS_AE_Grading_Table_v2_NOV2014.

Table 9-1: DAIDS AE Grading Table v2 General Guidelines

Grade	Description
Grade 1	indicates a mild event
Grade 2	indicates a moderate event
Grade 3	indicates a severe event
Grade 4	indicates a potentially life-threatening event
Grade 5	Death related to AE.

DAIDS AE Grading Table Version 2.0- November 2014

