7.2.4.1 Adverse Events

Adverse events will be classified by system organ class and preferred term (PT) according to the most recent MedDRA dictionary.

Since this is an extension of the PRO 140_CD 02 study, all adverse events (AE) that captured in this study will be considered as Treatment Emergent Adverse Events (TEAEs). The following TEAE summaries will be provided, using frequency counts and percentages:

- Overall (i.e., regardless of severity or relationship to treatment)
- By severity grade (mild, moderate, severe, life threatening or death)
- By relationship to study treatment

In addition, separate summaries of SAEs, and AEs resulting in discontinuation of study treatment will be presented.

Unless otherwise specified, at each level of subject summarization, a subject will be counted only once. If there is more than one occurrence of an event, the event of the worst severity or the worst-case relationship category will be summarized.

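### The named severe-AE outcome stops at Grade 4, so read literally it excludes a fatal (Grade 5) adverse event

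*Protocol*

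**What the plan says.** The outcome in Protocol 8.2 is "Frequency of Grade 3 or 4 adverse events as defined by the DAIDS Adverse Event scale". The synopsis, Protocol 2 and 8.7.4, and SAP 2.4 stop at the same grade.

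The scale in Protocol 9.1.3 (Table 9-1) runs one step further. Grade 4 "indicates a potentially life-threatening event", and Grade 5 is "Death related to AE". The SAP keeps the two apart as well; its planned TEAE summaries in 7.2.4.1 include "By severity grade (mild, moderate, severe, life threatening or death").

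SAP 7.2.4.1 also sets two counting rules. The first is a default of one count per subject at each level of the summary. The second concerns repeat occurrences, for which "the event of the worst severity or the worst-case relationship category will be summarized". The SAP gives no separate derivation for the Grade 3 or 4 outcome.

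Deaths are also reported elsewhere. SAP 7.2.4.1 states: "In addition, separate summaries of SAEs, and AEs resulting in discontinuation of study treatment will be presented". Protocol 9.2 makes death an SAE criterion. Protocol 8.2 lists treatment-emergent SAEs as its seventh measure, although SAP 2.4 does not carry that measure over.

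**The concern.** A severity outcome should not improve when a subject's event gets worse. Here the top category of the scale lies outside the outcome, and the SAP's default rule assigns each subject to the worst category reached. Together these can move a subject out of the severe-AE count at the point of death.

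This outcome is one of the named measures by which the study reports tolerability over open-ended treatment. Someone who quotes its single figure, without the by-grade table beside it, would take it to cover all severe events when it leaves out the fatal ones.

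**Working it through.** The documents state no expected rate of severe or fatal AEs and no sample-size calculation (Protocol 8.3, SAP 3), so there is no planned figure to reproduce. The check applies the written rules to a small example.

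**Inputs**
- N = 50, the maximum in the synopsis (planned number is up to 50).
- k = number of subjects with a Grade 3 or 4 event. This is an assumption; k = 3, 5 and 10 are shown.
- One of the k subjects has a Grade 4 event that becomes fatal. The documents do not say whether such an event is regraded in its record or entered as a second record, so both are tried.

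**Subject counted once at worst severity (SAP default).** The Grade 3 or 4 count goes from k to k − 1 under either record structure:
- k = 3: 3/50 = 6% becomes 2/50 = 4%
- k = 5: 5/50 = 10% becomes 4/50 = 8%
- k = 10: 10/50 = 20% becomes 9/50 = 18%

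The change is 1/N, so 1/50 = 2 percentage points. With fewer subjects it grows; for example, if 25 were enrolled it would be 1/25 = 4 points.

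**Other ways to count, with k = 5** (each subject has one severe event)

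| Counting rule | Event not fatal | Fatal, one record regraded 4 to 5 | Fatal, separate Grade 4 and Grade 5 records |
|---|---|---|---|
| Subject at worst grade, Grade 3 or 4 | 5 | 4 | 4 |
| Subject with any Grade 3 or 4 record | 5 | 4 | 5 |
| Events of Grade 3 or 4 | 5 | 4 | 5 (the Grade 5 record is not counted) |
| Subject with any Grade 3, 4 or 5 record | 5 | 5 | 5 |

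In the first three rows the Grade 5 record itself is never counted. Whether the total falls depends on the counting rule and the record structure. A subject whose only severe AE is entered directly as Grade 5 is missed under all three.

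**How often this could arise.** The chance of at least one fatal AE among 50 subjects is 1 − (1 − p)^50, where p is the per-subject risk. The documents give no p. Assumed values of 0.5%, 1%, 2% and 4% give 22%, 39%, 64% and 87%.

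**The case against.** The strongest reply is that the plan already reports deaths. The SAP severity summary has a death category beside the severe and life-threatening ones, a separate SAE summary is planned, and all data are listed by subject (SAP 7). This stands. A reader might infer that the plan conceals fatal events, and the documents do not support that. The omission of the SAE measure from SAP 2.4 is a separate defect and does not remove the SAE summary from 7.2.4.1.

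A second reply concerns the mechanism. The worst-severity sentence speaks of repeat occurrences of an event, the rule is a default, and the outcome's wording can be read as a count of events. Protocol 9.1.1 and 9.1.6 record grade and outcome as separate items and do not say how an event that turns fatal is regraded. This also stands in part. A reader might infer that every death lowers the count. That needs worst-grade subject counting or in-place regrading, and a subject who would otherwise have counted. The exclusion of the fatal event from the outcome does not depend on any of this; it follows from the definition alone.

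A third reply is that little rests on the measure. The study is single-arm, its primary objective is continued access, and Protocol 8.7.5 and SAP 7.2.4 plan no inference on safety data. Protocol 8.7.4 does mention a logit model for categorical measures, but attaches no hypothesis or threshold to this one. This limits the importance of the point. It does not make the definition sound.

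**Conclusion.** The point holds in a limited form. As written, the severe-AE outcome omits Grade 5, so any fatal AE is excluded from it. Under the SAP's default subject count, or if a Grade 4 record is regraded, a subject whose Grade 4 event becomes fatal also drops out. That is a shortfall of one subject per such case, or 2 percentage points at 50 subjects and more at lower enrollment. Under event counting with separate records, the Grade 4 record remains and only the fatal event is missing.

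The result is a named figure that understates the worst events whenever a fatal AE occurs. Deaths remain visible in the by-grade and SAE summaries, and no sample size, hypothesis or decision rule is affected. Whether any fatal event will occur cannot be judged from the documents.

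**What to change.** Restate the outcome as Grade 3 or higher in every place that lists it: the synopsis, Protocol 2, 8.2 and 8.7.4, and SAP 2.4. In SAP 7.2.4.1, add one sentence of derivation saying that a subject counts if any AE is Grade 3, 4 or 5. Keep the planned by-grade table, which already separates the three grades, so that the composition of the total can be seen.

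The cost is a change of wording in five lists and one added sentence. Grade and outcome are already collected for every AE (Protocol 9.1.1 and 9.1.6), so no new data are needed.

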8.3 SAMPLE SIZE DETERMINATION AND RATIONALE

Sample size determination is not applicable as only those subjects who are currently enrolled in PRO 140_CD 02 or CD02_OpenLabel study are allowed to participate in this study.

8.4 RANDOMIZATION AND BLINDING

No blinding or randomization requirement.

8.5 INTERIM ANALYSIS

No interim analysis planned.

8.6 GENERAL STATISTICAL CONSIDERATIONS

8.6.1 Analysis Populations

8.6.1.1 Safety Population

The Safety population is defined as the set of subjects who received at least one dose of PRO 140. This population will be used for the analysis of safety parameters.

8.6.2 Statistical Methods

All collected study data will be presented in subject data listings. Statistical analyses will be performed using SAS® for Windows, version 9.3 or later.

A SAP will be developed and approved before the database is locked. The SAP will present the detailed statistical methodology to be used in analyzing the safety data from this trial including details of appropriate statistical tests to examine underlying assumptions.

8.6.3 Prognostic Factors/Covariates

There are no pre-planned covariates analyses of the data from this study.

8.6.4 Handling of Missing Data

The methodology of imputing missing data, if applicable, will be detailed in the SAP.

8.7 DATA SUMMARY

8.7.1 Subject Disposition

The disposition of all subjects who sign an ICF will be provided. The number of subjects screened, received treatment, completed, and discontinued during the study, as well as the reasons for all post treatment discontinuations will be summarized. Disposition and reason for study discontinuation will also be provided as a by-subject listing.

8.7.2 Demographic and Baseline Characteristics

Demographics and baseline characteristics (i.e., Age, Gender, Time since HIV diagnosis, Viral load at T1, etc.) will be summarized using appropriate descriptive statistics.

Medical history of the subjects will also be provided as a by-subject listing.

8.7.3 Prior and Concomitant Medications

Prior and concomitant medications will be summarized for the Safety population. All prior and concomitant medications recorded in the eCRFs will be coded to generic term and all matching Anatomic Therapeutic Classification (ATC) codes using WHO Drug Summaries will be prepared using the coded terms. All prior and concomitant medications recorded in the eCRFs will also be listed.

8.7.4 Safety Measures

The following safety measures will be evaluated:

- Mean change in viral load (HIV-1 RNA levels) at the conclusion of the treatment period
- Mean change in CD4 cell count at the conclusion of the treatment period
- Emergence of Dual/Mixed (D/M)- and CXCR4-tropic virus in patients who had exclusive CCR5-tropic virus at study entry.
- Tolerability of repeated subcutaneous administration of PRO 140 as assessed by investigator-evaluation of injection site reactions
- Frequency of treatment-related adverse events resulting in study drug discontinuation
- Frequency of Grade 3 or 4 adverse events as defined by the DAIDS Adverse Event scale
- Frequency of treatment-emergent serious adverse events

All safety data measures will be summarized and tabulated according to the variable type:

- Continuous data summaries will include:
 - Number of observations, mean, standard deviation, median, and minimum and maximum values.
- Categorical data summaries will include:
 - Frequency counts and percentages.
 - Logit model will be used for inferential statistics.

8.7.5 Safety Analysis

The Safety population will be used for the analysis of safety assessments.

For continuous variables data will be summarized using n, mean, Standard Deviation (SD), minimum and maximum values. For categorical variables data will be summarized using frequency and percentage. No inferential statistics are planned.

8.7.5.1 Adverse Events

Adverse events will be coded using Medical Dictionary for Regulatory Activities (MedDRA). TEAEs are defined as events with an onset on or after the first treatment. TEAEs will be summarized by treatment group, System Organ Class, and preferred term. The following TEAE summaries will be provided:

- TEAEs by severity grade
- TEAEs by relationship to study treatment.

In addition, separate summaries of SAEs, and AEs resulting in discontinuation of study treatment will be presented.

8.7.5.2 Tolerability Assessment

All data from tolerability assessments of repeated subcutaneous administration of PRO 140 as assessed by investigator-evaluation of injection site reactions will be summarized.

8.7.5.3 Clinical Laboratory Data

All laboratory values will be listed. Laboratory measurements will also be summarized.

8.7.5.4 Physical Examination

All physical examination findings will be listed and any abnormality will be summarized.

8.7.5.5 Vital Signs

All vital sign assessment findings will be listed and summarized.

8.7.5.6 ECG Examination

All ECG examination findings will be listed and any abnormality will be summarized.

8.7.5.7 Neurological Assessment

All neurological assessment findings will be listed and any abnormality will be summarized.

9 ADVERSE EVENTS (DEFINITIONS AND REPORTING)

The Investigator is responsible for the detection and documentation of events meeting the criteria and definition of an AE or SAE, as provided in this protocol. During the study when there is a safety evaluation, the Investigator or site staff will be responsible for detecting, documenting, and reporting AEs and SAEs as detailed in this section of the protocol.

9.1 ADVERSE EVENT

An adverse event (AE) is defined as any unfavorable or unintended sign, symptom, or disease that occurs or is reported by the subject to have occurred, or a worsening of a pre-existing condition. An AE may or may not be related to the study treatment.

AEs will be elicited through direct questioning and subject reports. Any abnormalities in visit evaluations, physical examination findings or laboratory results that the Investigator believes are clinically significant to the research subject and that occurred after initiation of the first study treatment will be reported as AEs. Abnormal findings that are NOT clinically significant (NCS) should not be recorded as an AE.

9.1.1 Reporting of Adverse Events

Report initiation for all AEs and SAEs will begin at the time of the first treatment extension visit and continue up until the final study visit (i.e. up to NVF-FU2 for subject who do not experience virologic failure or until viral suppression is achieved for subjects who experience virologic failure). All events will be followed to resolution or until 30 days after the subject completes the study. A final assessment of outcome will be made at that time.

All AEs must be recorded in the subject's medical records and on the eCRFs. AEs will be reported using customary medical terminology along with the following information: the onset and end dates, whether the event is considered to be a SAE (see [Section 9.2](#)), the impact the event had on study treatment (see [Section 9.1.2](#)), the DAIDS AE grade (intensity) of the event (see [Section 9.1.3](#)), the causality of the event (see [Section 9.1.4](#)), whether treatment was given as a result of the event (see [Section 9.1.5](#)), and the outcome of the event (see [Section 9.1.6](#)).

